## STUDY PROTOCOL AND STATISTICAL ANALYSIS

Title of Study	Glycemic Control and Treatment Satisfaction Using Finesse Versus Pen for Initiating Bolus Insulin Dosing in Patients with Type 2 Diabetes Mellitus (T2DM) not Achieving Glycemic Targets on Basal Insulin With/Without Anti-Hyperglycemic Agents (AHA)
Devices	
 
• Finesse Bolus Insulin Delivery System cleared for commercialization in United States (US), Europe (EU), and Canada
 
• FlexPen® (aspart)
 
• SoloStar® Pen (glargine)
 

Study Purpose	In order to enable the Healthcare Provider (HCP) to more easily advance patients with T2DM sub-optimally controlled on basal insulin therapy to basal and bolus therapy, a novel bolus insulin patch ("Finesse") was developed by the Sponsor. The proposed study aims to determine whether initiating and managing bolus therapy with Finesse will result in non-inferior or improved glycemic control in patients with T2DM compared with a pen.

Study Objectives	
Primary Objective:
 
To compare the change in A1C, with bolus insulin dosing with Finesse versus pen, from baseline to the completion of 24 weeks of basal and bolus insulin therapy.
 
Secondary Objectives:
 
 
• To compare the change in other parameters of glycemic control with bolus insulin dosing with Finesse versus pen, from baseline to the completion of 24 weeks and 44 weeks of basal and bolus insulin therapy.
 
• To demonstrate that patient reported outcomes (PRO) improve with Finesse versus pen following the completion of 24 weeks and 44 weeks of basal and bolus insulin therapy.
 
• To demonstrate that HCPs prefer Finesse to pen for initiation of bolus insulin therapy following the completion of 24 weeks of basal and bolus insulin therapy by the last patient at their investigative site.
 

------------------	--

	
 
• To demonstrate the durability of effect of using Finesse and pen on maintenance of A1C from week 24 to week 44 of basal and bolus insulin therapy.
 
• To demonstrate that patients prefer Finesse to pen for bolus insulin therapy following a 4-week crossover from week 44 to week 48.
 

Study Design	
A randomized, open-label, 2-arm parallel study comparing glycemic control, patient satisfaction, and quality of life (QOL) of using Finesse versus pen to initiate and manage bolus insulin dosing in 312 patients, male and female, ages 22 to 75 years of age with T2DM not achieving glycemic targets on basal insulin with/without AHA. After a 4-week screening/baseline period, patients will be randomized 1:1 (balanced by study center) to either the Finesse arm or the pen arm to initiate bolus insulin using a simple bolus dosing algorithm and followed for a 44-week intervention period. After the final endpoint evaluation at week 44, patients will crossover to the alternate bolus insulin delivery device for 4 weeks and complete a patient preference survey at week 48.
 
The study will be conducted in the following periods: Screening Visit 1 (Week -4 to -3); Baseline Visit 2A (Week -2); Randomization Visit 3 (Week 0) to include insulin dosage optimization;i,1 Phone Calls Insulin Titration (Weeks 1, 2, 3, 6, 8); Follow-up Visits 4 (Week 4), 5 (Week 12), 6C (Week 24), 7 (Week 36), 8 (Week 44), and 9 (Week 48). Visits 2B (Week -1), 6A (Week 22), and 6B (Week 23): Only the subset of patients performing continuous glucose monitoring (CGM) (50 patients per arm) will have additional visits for performing blinded CGM assessments.

Study Sites	A multicenter study (approximately 50 sites). Sites and patients will be approximately divided between the US and EU.
Patient Population	A total of approximately 312 enrolled adults, male and female, aged 22-75 years, body mass index of $\leq 40 \text{ kg/m}^2$ , with T2DM not achieving glycemic targets (A1C 7.5-11.0%)

i Educational materials specifically designed for this study based on the International Diabetes Center simple algorithm for adjustment of insulin in Type 2 diabetes. Patients will record SMBG before meals and bedtime, and insulin doses.

	using basal insulin ( $\geq 0.3$ U/kg/day) with/without AHA based on the participant's medical needs.
Duration of Patient Participation	Total duration of participation by each patient is expected to be approximately 52 weeks.
Dosage and Administration	
At randomization, total daily dose (TDD) of insulin will be divided as 50:50, basal: bolus (Note: For those subjects with a screening A1C of <math><9\%</math>, the TDD is to be reduced by 10% prior to splitting the dose 50:50, basal: bolus, in order to avoid potential for hypoglycemia at institution of new regimen). Basal insulin therapy for each group will be titrated using a simple algorithm by chart to adjust by 2U increments to achieve pre-morning meal fasting plasma glucose (FPG) target of 71-130 mg/dl (4.0-7.2 mmol/l). Bolus insulin dosing will start with fixed pre-meal doses (divided equally between morning meal, midday meal, and evening meal). Prandial insulin therapy for each group will be titrated using a simple algorithm by chart to adjust by 2U increments based on pre-midday meal and pre-evening meal self-monitoring blood glucose (SMBG) target of 71-130 mg/dl (4.0-7.2 mmol/l) and bedtime SMBG target of 71-130 mg/dl (4.0-7.2 mmol/l): pre-morning meal dose will be titrated based on pre-midday meal SMBG; pre-midday meal dose will be titrated based on pre-evening meal SMBG; pre-evening meal dose will be titrated based on bedtime SMBG. For basal insulin, all patients will use Lantus® (Glargine) by a pen (SoloStar®) before evening meal or at bedtime. For bolus insulin, patients will use Finesse containing rapid-acting NovoLog®/NovoRapid® (Aspart) or the FlexPen®. Patients will discontinue the following AHA: Sulfonylureas, Meglitinides, GLP-1 agonists, bromocriptine, and DPP-4 inhibitors that have not been studied in combination with insulin, namely, saxagliptin and linagliptin. Patients on the following AHAs will continue them in their current doses: Biguanides, Alpha-glucosidase inhibitors, SGLT2 inhibitors, Thiazolidinediones, and DPP-4 inhibitors that have been studied and approved for use in combination with insulin, namely, sitagliptin, alogliptin, and vildagliptin.

Endpoint Evaluation at Week 24	
Primary Endpoint	Change in A1C from baseline to week 24, comparing Finesse versus Pen.
Secondary Endpoints	
 
• Proportion of patients with A1C <math>\leq 7.0\%</math> at week 24;
 

	
 
• Change in percent of glucose values of CGM measurements (in a subset of patients) within targeted range of 71 and 180 mg/dl (4.0 and 10.0 mmol/l) from a one or two week period of week -2 to week 0 (baseline) to a one or two week period of week 22 to week 24;
 
• Change in 3-day average 7-point SMBG from baseline to week 24;
 
• Change in 3-day coefficient of variation (CV) of 7-point SMBG from baseline to week 24;
 

Tertiary Endpoints	
 
• Change in A1C from baseline to week 12;
 
• Change in average glucose values of CGM measurements (in a subset of patients) from a one or two week period of week -2 to week 0 (baseline) to a one or two week period of week 22 to week 24.
 
• Change in percent of glucose values of CGM measurements (in a subset of patients) <math>\leq</math> 70 mg/dl (<math>\leq</math> 3.9 mmol/l) and percent of values <math>></math> 180 mg/dl (<math>></math> 10.0 mmol/l) from a one or two week period of week -2 to week 0 (baseline) to a one or two week period of week 22 to week 24;
 
• Change in FPG from baseline to week 24;
 
• Change in 3-day insulin doses (total daily dose, basal dose, bolus dose) from baseline to week 24.
 

Patient Reported Outcomes	
 
• Change in treatment satisfaction for insulin delivery from baseline to week 24;
 
• Change in patient quality of life from baseline to week 24;
 
• Patient experience survey at week 24;
 
• Patient insulin usage survey at week 12 and 24.
 

Healthcare Provider Reported Outcomes	
 
• HCP experience survey at week 24.
 

Endpoint Evaluation at Week 44	
Secondary Endpoints	
 
• Change in A1C from baseline to week 44;
 
• Proportion of patients with A1C <math>\leq</math> 7.0% at week 44;
 
• Change in 3-day average 7-point SMBG from baseline to week 44;
 
• Change in A1C from week 24 to week 44.
 

Tertiary Endpoints	
 
• Change in A1C from baseline to week 36;
 
• Change in 3-day CV of 7-point SMBG from baseline to week 44.
 
• Change in FPG from baseline to week 44;
 

	
 
Change in 3-day insulin doses (total daily dose, basal dose, bolus dose) from baseline to week 44.
 

Patient Reported Outcomes	
 
Patient experience survey at week 44;
 
Patient insulin usage survey at week 36 and 44.
 

Endpoint Evaluation at Week 48	
Patient Reported Outcomes	
 
Patient preference survey at week 48.
 

Safety Observations	
 
Incidence and rate of severe hypoglycemiaii,3
 
Incidence and rate of non-severe hypoglycemia (<math>\leq 70</math> mg/dl) (<math>\leq 3.9</math> mmol/l) (both symptomatic and asymptomatic);
 
Incidence of all adverse events;
 
Incidence of serious adverse events;
 
Incidence of adverse device effects;
 
Incidence of serious adverse device effects;
 
Discontinuation rate due to adverse events.
 
Incidence of clinically important changes in clinical laboratory tests, vital signs (pulse, blood pressure), physical examination, and body weight.
 

Data Analysis	
Analysis Sets
 
The intent-to-treat (ITT) analysis set includes all patients who initiated bolus insulin therapy. The modified intent-to-treat (mITT) analysis set includes all the ITT patients who had a baseline and at least one post-baseline A1C measurement. The per protocol (PP) analysis set consists of all mITT patients who complete the 24-week efficacy phase, and have no major protocol deviations that may affect the interpretation of the primary efficacy endpoint. Efficacy measurements will be summarized for both mITT and PP analysis sets; the primary efficacy analyses will be based on the mITT analysis set. The ITT set will be used for all safety analyses.
 
Sample Size Determination

ii Severe hypoglycemia is defined as an event requiring the assistance of another person to actively administer carbohydrate (including IV dextrose), glucagon, or other resuscitative actions. These episodes may be associated with sufficient neuroglycopenia to induce seizure or coma. Neurological recovery attributable to the restoration of plasma glucose to normal is considered sufficient evidence that the event was induced by a low plasma glucose concentration.

The sample size determination is based on the primary endpoint, A1C change from baseline to Week 24. Assuming that the true mean difference in A1C change (Finesse vs Pen) is -0.1% with a SD 1.2%, a study population of 250 completers (125 per arm) is required to achieve a power of 90% for non-inferiority with a margin of 0.4%, i.e., the upper bound 2-sided 95% confidence interval of the difference in mean A1C change (Finesse vs Pen) is less than 0.4%. Assuming a discontinuation rate of 20% (for the 24 week primary endpoint analysis), the number of patients to be enrolled =  $250/(1-0.20) = 312$  patients (156 per arm).

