#### Efficacy Analysis Plan

Differences between arms (Finesse arm versus pen arm) at week 24 will be analyzed using analysis of covariance (ANCOVA) model with the baseline A1C value as the covariate; the 2-sided 95% confidence interval of the difference will be computed using the model. The non-inferiority of Finesse to pen will be concluded if the upper bound of the 95% 2-sided confidence interval for change in A1C is less than the inferiority margin of 0.4%. This test is the same as a 1-sided test with an alpha of 0.025. Superiority of Finesse will be tested if non-inferiority is shown.

Each of the secondary and tertiary endpoints at week 24 and week 44 will be tested for superiority of the Finesse arm to the pen arm, but the tests will be interpreted inferentially only if non-inferiority is demonstrated with respect to the primary endpoint. Otherwise, the p-values and 95% confidence intervals for the secondary and tertiary endpoints will be considered to be nominal. The continuous endpoints will be analyzed using the same ANCOVA model described for the primary endpoint. The categorical endpoints will be analyzed using a Cochran-Mantel-Haenszel test. The Type 1 error rate will be at 0.05.

To evaluate durability of effect of using Finesse versus pen, change in A1C from 24 week to 44 week will be analyzed by treatment groups using t-test for each treatment arm.

Other general considerations for the statistical analysis will include descriptive statistics (sample size, mean, SD, median, minimum, and maximum) for continuous variables and 95% CI of the mean, and, where appropriate, the percentage values for categorical variables, and tests of significance between treatment arms including p-value and 95% CI.

Additional Analyses

Analyses will also be performed to examine the relationships between variables known to be associated. In particular, the relationship between A1C and severe hypoglycemiaiii, the relationship between A1C and weight change, and the relationship between A1C and adherence measures will be described in each group. These analyses will be descriptive, primarily using categorical cross-classifications to examine whether any shifts in hypoglycemia, weight change, or adherence measures are consistent with expected changes due to improved glycemic control.

---

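### Some patients must stop a glucose-lowering drug and others stop none, but the primary ANCOVA does not adjust for this: a cheap gain in precision is missed, with no threat to validity

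*Combined protocol and SAP*

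**What the plan says.** The Patient Population section admits patients on basal insulin "with/without AHA based on the participant's medical needs". The Dosage and Administration section then divides them by rule. For one list, "Patients will discontinue the following AHA: Sulfonylureas, Meglitinides, GLP-1 agonists, bromocriptine, and DPP-4 inhibitors that have not been studied in combination with insulin" (the last group being saxagliptin and linagliptin). For the other list, which includes biguanides, SGLT2 inhibitors, thiazolidinediones and three named DPP-4 inhibitors, "Patients on the following AHAs will continue them in their current doses". Patients on no AHA have nothing to stop.

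The Study Design section states that "patients will be randomized 1:1 (balanced by study center"; no other randomisation factor is named. The primary endpoint is "Change in A1C from baseline to week 24, comparing Finesse versus Pen". The Efficacy Analysis Plan specifies an "analysis of covariance (ANCOVA) model with the baseline A1C value as the covariate" and applies the same model to the continuous secondary and tertiary endpoints at weeks 24 and 44. No stratum, covariate, subgroup or sensitivity analysis for AHA withdrawal appears.

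**The concern.** Take two patients with the same baseline A1C, one of whom loses a glucose-lowering drug under the protocol. If the baseline value was obtained while that drug was still acting, their expected changes to week 24 may differ, and baseline A1C cannot tell them apart. The difference then stays in the residual, where it widens the interval for the treatment difference. In any single trial, a chance imbalance in the share of patients stopping a drug moves the Finesse-minus-pen estimate a little, in one direction or the other.

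What is at stake is precision in the non-inferiority comparison and in the other continuous endpoints that share the model. There is also a matter of timing. The trial is open-label, so a covariate added after an imbalance has been seen would look chosen by the data. Pre-specified, it raises no such question.

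**Working it through.** **Inputs from the documents** (Sample Size Determination and Efficacy Analysis Plan): true difference -0.1%, SD 1.2%, margin 0.4%, one-sided alpha 0.025, power 90%, 125 completers per arm, 20% discontinuation.

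**Inputs assumed**, because the documents do not give them: share p of patients who must stop an AHA, 0.10-0.50; effect b of stopping on A1C change, 0.3-0.8%.

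**Step 1. The plan's own figure.** The distance from the assumed truth to the margin is 0.4 + 0.1 = 0.5.
- n per arm = 2(1.960 + 1.282)² × 1.44 / 0.5² ≈ 121.04, rounded up to 122. The stated 125 is slightly generous.
- SE at 125 per arm = 1.2 × √(2/125) = 0.152, so the 95% half-width is 1.96 × 0.152 ≈ 0.30.
- Power = Φ(0.5/0.152 − 1.96) = 90.9%.
- Enrolment: 250/0.8 = 312.5, stated as 312.

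The sample size reproduces.

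**Step 2. Effect of adjusting.** The planned SD is taken to include the AHA variation.
- Share of variance explained = p(1−p)b²/1.44
- Adjusted SD = √(1.44 − p(1−p)b²)
- 95% chance imbalance in the share stopping = 1.96 × √(2p(1−p)/125)
- Chance shift in the treatment difference = b × that imbalance

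| p | b | Variance explained | Imbalance (95%) | Shift (A1C %) | Adjusted SD | Power after adjustment |
|---|---|---|---|---|---|---|
| 0.10 | 0.3 | 0.6% | 7.4 points | 0.022 | 1.197 | 91.0% |
| 0.30 | 0.5 | 3.6% | 11.4 points | 0.057 | 1.178 | 91.9% |
| 0.50 | 0.8 | 11.1% | 12.4 points | 0.099 | 1.131 | 93.7% |

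The half-width falls from 0.2975 to 0.2975 × √(1 − 0.0056) = 0.297 in the first row, and to 0.2975 × √(1 − 0.111) = 0.281 in the last.

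**Step 3. Validity without adjustment.** Simulation of 20,000 trials per scenario, with and without the covariate:

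| p, b | Type I error: unadjusted / adjusted | Power: unadjusted / adjusted |
|---|---|---|
| 0.3, 0.5 | 0.025 / 0.024 | 90.7% / 91.6% |
| 0.4, 0.8 | 0.026 / 0.026 | 90.6% / 93.6% |
| 0.5, 1.0 (beyond the range above) | 0.025 / 0.027 | 90.4% / 94.8% |

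The simulation error on a rate of 0.025 is √(0.025 × 0.975/20,000) ≈ 0.001. The unadjusted test keeps its level and its planned power.

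**Step 4. If 1.2% does not cover the mixed population.** The documents do not say where the SD comes from. If the AHA variation comes on top of it, the total variance at p = 0.5, b = 0.8 is 1.44 + 0.16 = 1.60. The SE is then √(1.60 × 2/125) = 0.160 and unadjusted power is Φ(0.5/0.160 − 1.96) = 87.8%. At p = 0.1, b = 0.3 the total variance is 1.448, the SE is 0.1522 and power is 90.7%. Adjustment would return either to 90.9%.

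**The case against.** The strongest reply is that nothing here is an error. Randomisation leaves baseline factors to chance, and the confidence interval exists to cover the result. Step 3 bears this out. The calculation in Step 2 takes the AHA variance out of the planned 1.2%, so the shift of 0.02-0.10 is already part of the half-width of 0.30. Setting it against the 0.4% margin as an additional risk would count it twice. A reader might infer that chance imbalance could decide the non-inferiority conclusion for reasons unrelated to the device, or that the comparison is biased. The documents support neither reading. An adverse imbalance at its 95% limit would lower conditional power (to about 84% in the middle row of Step 2), but a favourable one is equally likely, and the average over randomisations is the planned figure.

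A reader might also infer that AHA withdrawal is an established driver of A1C change in this trial. The documents do not say so. They give no effect size and no share. The discontinuation sentence carries no date: it stands in a section that opens with randomisation, after a 4-week screening and baseline period, so whether baseline A1C is measured on the drug is not stated. Titration may also offset the lost drug: "Prandial insulin therapy for each group will be titrated using a simple algorithm by chart", and basal insulin is likewise titrated, to common glucose targets in both arms. All of this stands, and it means the true gain could be close to nil.

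Two further objections stand in part. Other baseline variables could be proposed on the same argument. This one differs in that the protocol itself imposes the change of regimen on some patients and not on others. A single yes/no flag also pools drugs whose withdrawal may have different effects. That limits how much variance it explains but does no harm to validity.

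The objections reduce the size of the point but do not remove it. If titration offsets the withdrawal in A1C, the effect should appear instead in change in insulin dose, a tertiary endpoint analysed with the same model.

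**Conclusion.** The structure is confirmed: a rule-based split in AHA withdrawal, centre as the only stated randomisation factor and baseline A1C as the only stated covariate. The consequence is a modest, inexpensive gain in precision that the plan forgoes. The primary analysis is valid as written. Under the assumed share of 10-50% and effect of 0.3-0.8% A1C, adjustment raises power from 90.9% to about 91-94% and narrows the half-width by about 0.001-0.017% A1C. These figures take the 1.2% SD as covering the mixed population; if it does not, adjustment recovers up to about 3 points of power (87.8% to 90.9%). At the low end of either assumption the gain is negligible. The point is a recommendation, worth adopting because it costs so little.

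**What to change.** Add one sentence to the Efficacy Analysis Plan: the primary ANCOVA includes, besides baseline A1C, a fixed yes/no factor for whether the patient is required to discontinue an AHA under the protocol list, and the same factor enters the model for the other continuous endpoints. Define it from medication use recorded before randomisation, and by what the list requires rather than by what the patient later does, so that it stays a baseline variable.

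The cost is one derived variable and one degree of freedom, with no extra patients. The synopsis does not describe the medication record, but sites must know each patient's AHA use to apply the stop and continue lists.

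I do not recommend balancing on the factor at randomisation. The Study Sites section has "A multicenter study (approximately 50 sites", so 312/50 gives about 6 patients per centre, and splitting each centre again would leave strata of about 3 at best. No change to which drugs are stopped or continued, or when, is proposed.

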#### Efficacy Analysis Plan

Differences between arms (Finesse arm versus pen arm) at week 24 will be analyzed using analysis of covariance (ANCOVA) model with the baseline A1C value as the covariate; the 2-sided 95% confidence interval of the difference will be computed using the model. The non-inferiority of Finesse to pen will be concluded if the upper bound of the 95% 2-sided confidence interval for change in A1C is less than the inferiority margin of 0.4%. This test is the same as a 1-sided test with an alpha of 0.025. Superiority of Finesse will be tested if non-inferiority is shown.

Each of the secondary and tertiary endpoints at week 24 and week 44 will be tested for superiority of the Finesse arm to the pen arm, but the tests will be interpreted inferentially only if non-inferiority is demonstrated with respect to the primary endpoint. Otherwise, the p-values and 95% confidence intervals for the secondary and tertiary endpoints will be considered to be nominal. The continuous endpoints will be analyzed using the same ANCOVA model described for the primary endpoint. The categorical endpoints will be analyzed using a Cochran-Mantel-Haenszel test. The Type 1 error rate will be at 0.05.

To evaluate durability of effect of using Finesse versus pen, change in A1C from 24 week to 44 week will be analyzed by treatment groups using t-test for each treatment arm.

Other general considerations for the statistical analysis will include descriptive statistics (sample size, mean, SD, median, minimum, and maximum) for continuous variables and 95% CI of the mean, and, where appropriate, the percentage values for categorical variables, and tests of significance between treatment arms including p-value and 95% CI.

Additional Analyses

Analyses will also be performed to examine the relationships between variables known to be associated. In particular, the relationship between A1C and severe hypoglycemiaiii, the relationship between A1C and weight change, and the relationship between A1C and adherence measures will be described in each group. These analyses will be descriptive, primarily using categorical cross-classifications to examine whether any shifts in hypoglycemia, weight change, or adherence measures are consistent with expected changes due to improved glycemic control.

---

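### The primary set includes patients with only a week-12 A1C, but the plan does not say how they enter the week-24 ANCOVA, and no planned analysis would show the effect of selective loss

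*Combined protocol and SAP*

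**What the plan says.** The primary endpoint is "Change in A1C from baseline to week 24, comparing Finesse versus Pen" (Endpoint Evaluation at Week 24). Under Efficacy Analysis Plan, "Differences between arms (Finesse arm versus pen arm) at week 24 will be analyzed using analysis of covariance (ANCOVA) model", with baseline A1C as the covariate. The upper limit of the two-sided 95% interval is compared with 0.4%.

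Under Data Analysis, Analysis Sets, "the primary efficacy analyses will be based on the mITT analysis set". That set "includes all the ITT patients who had a baseline and at least one post-baseline A1C measurement". A week-24 value is not a condition of entry. An earlier A1C does exist, because the tertiary endpoints include "Change in A1C from baseline to week 12". The only other efficacy set, per protocol (PP), "consists of all mITT patients who complete the 24-week efficacy phase" and who have no major deviations bearing on the primary endpoint.

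Under Sample Size Determination, "a study population of 250 completers (125 per arm) is required to achieve a power of 90"%, and enrolment is raised to 312 for 20% discontinuation before the primary endpoint.

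The document states no imputation, carry-forward rule, repeated-measures model or estimand. It does not say whether A1C is collected after a patient stops, and it plans no missing-data sensitivity analysis.

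**The concern.** A patient who leaves between weeks 12 and 24 is in the declared primary set but has no outcome for the declared model. Standard ANCOVA software drops such a patient. The mITT analysis then covers only those with an observed week-24 A1C, largely the same people as PP. Agreement between the two would say little about robustness, because both omit the same patients.

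The trial is open-label, so leaving because of the device is plausible. Enrolling extra patients restores precision but does not remove bias from selective loss. The superiority test, and any inferential reading of the secondary and tertiary endpoints, depend on the primary non-inferiority result. With the method unstated, the choice between observed-case, carry-forward and model-based analysis could also be made after the data are seen.

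**Working it through.** **Inputs from the plan.** True difference -0.1 and SD 1.2 ("Assuming that the true mean difference in A1C change (Finesse vs Pen) is -0.1% with a SD 1.2"%); margin 0.4; one-sided alpha 0.025; 125 completers per arm; 312 enrolled; 20% discontinuation. Differences are in A1C percentage points, Finesse minus pen, so positive is worse for Finesse.

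**The plan's own figure.** n per arm = 2 × 1.2² × (1.960 + 1.282)² / (0.4 + 0.1)² = 121.05, so 122, against 125 stated. At 125 per arm, SE = 1.2 × √(2/125) = 0.152, and power = Φ(0.5/0.152 − 1.96) = 90.9%. Enrolment: 250/0.80 = 312.5, against 312. The sample size reproduces.

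**Expected result under the plan's assumptions.** Upper bound = −0.1 + 1.96 × 0.152 = 0.198, about 0.20. Non-inferiority passes if the observed difference is below 0.4 − 0.298 = 0.102.

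**Effect of omitting missing patients.** Let m be the fraction missing in each arm (taken as equal). Let D be the amount by which missing Finesse patients are worse than observed Finesse patients, minus the same quantity for pen (assumption). Then:

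- Difference in all patients = observed-case difference + m × D.
- One-sided error at a true all-patient difference of 0.4 = Φ(−1.96 + m × D / 0.152), with 125 observed per arm.
- D at which the expected bound reaches 0.4 = (0.4 − 0.198)/m.

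| Missing per arm (assumption) | m | Error, D = 0 | Error, D = 0.5 | Error, D = 1.0 | D at which bound reaches 0.4 |
|---|---|---|---|---|---|
| 10 of 135 | 7.4% | 2.5% | 4.3% | 7.1% | 2.7 |
| 20 of 145 | 13.8% | 2.5% | 6.6% | 14.7% | 1.5 |
| All assumed discontinuation | 20% | 2.5% | 9.7% | 26% | 1.0 |

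The first two rows describe mITT patients without a week-24 value. The third is an upper scenario. It counts every discontinuation, including patients who never had a post-baseline A1C and so are outside mITT.

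**Unequal dropout.** If non-completers are worse than completers by g in both arms, the shift is (difference in dropout fractions) × g. For 25% against 15%, g = 0.5 gives 0.10 × 0.5 = 0.05. For 30% against 10%, g = 1.0 gives 0.20 × 1.0 = 0.20.

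**Gain from using week 12.** With k partial patients per arm and correlation r between week-12 and week-24 changes, the variance of the week-24 mean is multiplied by about 1 − r² × k/(125 + k). For k = 10 to 20 and r = 0.6 to 0.8 (assumptions), power rises from 90.9% to between 91.6% and 93.2%.

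**A penalised sensitivity analysis.** Adding 0.4 to imputed Finesse values with 20% imputed shifts the estimate by 0.20 × 0.4 = 0.08. Expected bound = 0.198 + 0.08 = 0.278, about 0.28. Power = Φ((0.4 + 0.1 − 0.08)/0.152 − 1.96) = 79%, keeping SE at 0.152 as an approximation.

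**The case against.** The strongest reply is that this is an unstated rule, not an incompatibility. ANCOVA on mITT works once an imputation rule is written down, and powering on completers and then inflating for dropout is ordinary practice. Both points stand. The completer count may hint that an observed-case analysis was meant, but the plan does not say so, and that reading would leave mITT almost the same as PP.

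A reader might infer that the model discards 20% of the primary set. The documents do not support this. The 20% is discontinuation among all enrolled patients. Some would leave before any post-baseline A1C and so are not in mITT, and others might stop treatment yet still have a week-24 value. The split is not given.

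A reader might also infer that the omission favours Finesse. That does not follow. Pen patients doing badly may leave too, which would bias against Finesse, and if missing patients are equally worse in both arms with equal dropout the shift is zero.

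Nor does a repeated-measures model cure selective loss. It assumes data are missing at random and gains only about 1 to 2 points of power. What remains is that a usable week-12 value has no stated role in the primary analysis, and nothing planned tests sensitivity to loss.

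**Conclusion.** The gap is real and the plan should close it, although the design and sample size are sound. The declared primary set contains patients for whom the declared model has no outcome, no rule covers them, and the second efficacy set cannot reveal selective loss because it is also confined to those who complete 24 weeks.

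The bias is conditional. The tabulated error rates rest on assumed missing fractions and on an assumed relative worsening in missing Finesse patients. The 7-14% rows match the mismatch between set and model. The 9.7%, 26% and 1.0-point figures are an upper scenario and should not be read as expected values. The documents establish neither a direction nor a size.

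**What to change.** In Efficacy Analysis Plan, state that the primary week-24 contrast includes mITT patients without a week-24 A1C by a method that uses their week-12 value. Either of two would serve:

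- a repeated-measures model of A1C change at weeks 12 and 24 with arm, visit, arm-by-visit and baseline A1C, reading the week-24 contrast against 0.4%; or
- the existing ANCOVA after multiple imputation that uses week 12.

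Keep the observed-case ANCOVA as supportive.

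Because both methods assume missing at random, add a sensitivity analysis in all patients who initiated bolus therapy (the plan's ITT set): multiple imputation with 0.4% added to imputed Finesse values, and a tipping-point table that varies the assumption in both arms.

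The cost is SAP wording and modest programming, with no new data. The penalised analysis will be less favourable: an expected bound of about 0.28 and power of about 79%, under the plan's assumptions with 20% imputed. The choice should be fixed before week-24 results are compared by arm.
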